6.3 PRIOR AND CONCOMITANT MEDICATIONS

All treatments being taken by the subjects at study entry, or within 30 days prior to first study treatment administration, or at any time during the study in addition to the investigational product are regarded as concomitant medications and must be documented on the appropriate pages of the CRF.

6.3.1 Forbidden concomitant medications / treatments

- Concurrent treatment (or within 30 days, or 5 half-lives, whichever is longer) with other investigational drugs.
- Concurrent treatment (or within 21 days) with any anticancer therapy including chemotherapy, immunotherapy, hormone therapy, or biological therapies, other than those specified in the protocol. The only exception is hydroxyurea given to control hyperleukocytosis that can be continued until 48 hours before OTX015/MK-8628 treatment initiation, but must be stopped at that time; Furthermore, should rapidly increasing white blood cell count occur during the first cycle of OTX015/MK-8628, hydroxyurea could be given not earlier than day 3 and not beyond day 43 for the shortest period as clinically indicated to control hyperleukocytosis and keep the patient on study. At day 43 the decision to start OTX015/MK-8628 cycle 3 will be taken by the investigator according to patient's anticipated benefit but without hydroxyurea. If, nonetheless, hydroxyurea has to be resumed during cycle 3, this would be considered as OTX015/MK-8628 treatment failure and the patient would be withdrawn from the study.
- Prophylactic anti-emetic drugs or other drugs given with a prophylactic intent at the first cycle, unless the SMC decides to deliver systematic premedication.
- Corticosteroid, except chronic treatment with ≤ 30 mg/day of methymprednisolone or equivalent.
- Concurrent treatment with drugs with potential interaction: No drug interaction study has been undertaken with OTX015/MK-8628 so far. However, OTX015/MK-8628 has been shown to inhibit CYP3A4 and CYP2A6. Thus, patients using concomitant drugs or other substances

interfering with these CYP450 species (see Appendix XI, section 16.11) should be followed-up carefully for possible potentialization/inhibition of effects of OTX015/MK-8628 and/or concomitant substance. In addition, concomitant treatment with strong (see Appendix XI, section 16.11) CYP3A4 interacting drugs is prohibited. Note that as these lists are not comprehensive, the investigator should use his/her medical judgment when a patient presents with a medication not on the list or call the Sponsor Medical Expert for clarification.

6.3.2 Allowed concomitant medications / treatments

- Supportive treatment of symptoms/adverse events or standard treatment of concomitant conditions, especially transfusion support and antibiotics, bisphosphonates will be given as medically indicated and reported in the CRF.
- 7 Patients on anticoagulant or antiaggregant (including low-dose aspirin) therapy at screening for concomitant medical conditions should be evaluated in coordination with their cardiologist for the benefit/risk ratio of continuing their anticoagulant or antiaggregant therapy during study due to the potential increased risk of bleeding in case of occurrence of severe thrombocytopenia. Blood cell count should be more frequently performed in such patients, at least weekly during the whole study, and more in case of grade 2 to 3 thrombocytopenia. Study procedures and schedule.

7.2 DESCRIPTION OF STUDY DAYS

7.2.1 Pre-study screening

Each potential subject will be examined before the start of the study to determine their eligibility for participation. These tests are to be conducted within 7 days prior to the first study treatment administration, except tumor imaging, bone marrow biopsy and LVEF measurement that can be performed within 30 days and informed consent, and fresh tumor cell sampling that should be obtain within 14 days prior to the first study treatment administration.

The following investigations will be performed:

PARAMETERS	INVESTIGATIONS	TIMING					
1.Informed consent	Obtain written subject informed consent prior to any specific study procedure	Within 14 days * prior to registration					
2. Medical history	Diagnosis of hematological malignancy; prior anticancer therapies; Non cancer medical history; Concurrent illness; concomitant medications.	Any time before registration					
3. Pregnancy test	Blood or urine tests unless menopause is proven (age > 50 and last menarches > 3 years, or menopausal hormone levels, or surgical castration)	Within 7 days * prior to first administration					
4. Clinical Examination	4. Clinical Examination Height and weight, vital signs, ECOG PS, clinical tumor measurement, and Physical examination.						
5. Cardiac function	ECG Echocardiography (LVEF measurement)	Within 7 days * Within 30 days * prior to first administration					
6. Existing signs and symptoms	Baseline evaluation (to document residual toxicity from previous therapy, and baseline symptoms) graded according to NCI-CTCAE.	Within 7 days * prior to first administration					
7. Hematology (peripheral blood)	CBC with platelets counts, WBC differential and hemoglobin, INR.	Within 7 days * prior to first administration (including day 1)					
8. Hematology (bone marrow aspiration)	for patients with AL** and MM	Within 7 days * prior to first administration					
9. Biochemistry	LDL, HDL, β2-microglobulin (for patients with myeloma), Alkaline phosphatases (AP), LDH, CPK, CRP, ASAT, ALAT, total bilirubin, serum creatinine, ionogram (sodium, potassium, chloride, HCO3-), calcium, phosphorus, magnesium, total protein, albumin, glucose, Apo A1.	Within 7 days * prior to first administration					
10. Urinalysis	Dipstick for blood, glucose and albumin	Within 7 days * prior to first administration					
9. Tumor assessment/imaging	CT-scan or MRI (baseline) if evaluable tumor masses; PET-scan if deemed necessary for proper response assessment; skeletal X-ray/MRI in multiple myeloma	Within 30 days ** prior to first administration					
	Bone marrow biopsy if necessary for tumor assessment						
10. Fresh tumor cell collection for biomarkers and intracellular PK	Serum M-component or BJ proteinuria (for patients with MM) Fresh tumor biopsy of superficial lymph nodes, or blood/bone marrow for leukemia	Within 14 days * prior to first administration					
11. Other Investigations	Others as clinically or biologically indicated.	Within 7 days * prior to first administration					

*In case of delay in the planned first study treatment administration, the tests should be repeated, or the ICF resigned.

**Routine imaging and bone marrow biopsy performed outside of the scope of this study will be acceptable for baseline data, if performed \leq 30 days prior to study entry

***Screening bone marrow aspiration for patients with AL will include cytology, cytogenetics and 3mL to be kept for cellular PK/PD and predictive factors.

The information in this document is the property of OncoEthix and is confidential. Neither the document nor the information contained therein may be reproduced or disclosed outside OncoEthix without their written consent

7.2.2 Evaluation during each study visit during study treatment

PARAMETERS	INVESTIGATIONS	TIMING
1. Clinical Examination	Weight, vital signs, ECOG PS, clinical tumor measurement, and physical examination. Concurrent illness; concomitant medications,	Before study treatment administration. In addition, on days 1, vital signs will be recorded, 1 and 2 hours after administration, in order to capture possible peak effects
2. ECG	ECG	Only on days 1 and 22 : Before study treatment administration, then on day 1 only at 1 and 2 hours after administration , in order to capture possible peak effects
3. Adverse Events*	Adverse events Serious adverse events have to be declared up to 30 days after last OTX015/MK-8628 intake regardless of relationship with study drugs and beyond if drug related.	Before study treatment administration Within 24 working hours
4. Hematology**	CBC with platelets counts, WBC differential and hemoglobin, INR. Bone marrow aspiration for patients with leukemia and myeloma	Before study treatment administration Only on day 1 (if not done at screening) then on days 8 ^{§,} 22 and 43 (for AL). For myeloma, mandatory only to confirm CR), then at the investigator's discretion
	Bone marrow aspiration in all patients	In case of grade 4 thrombocytopenia lasting > 3 days
5. Biochemistry***	LDL, HDL, β2-microglobulin (for patients with myeloma), AP, LDH, CPK, CRP, ASAT, ALAT, total bilirubin, serum creatinine, ionogram (sodium, potassium, chloride, HCO3-), calcium, phosphorus, magnesium, total protein, albumin, glucose. Apo A1	Before study treatment administration Only at day 22 for Apo A1
6. Urinalysis	Dipsticks for albumin, blood and glucose	Before study treatment administration
7. Pharmacokinetics	Plasma sampling. Please, refer to the sampling schedule (section 7.3.3.1).	Only on Days 1,-2 (complete PK) or 1 (limited sampling)- , then days 8, 15 and 22 (all patients)
8. Optional fresh tumor cell sampling for biomarkers and intracellular PK for patients with other hematological malignancies	Biopsy of superficial lesion	Day 1 (or within 14 days prior to first study drug administration) and Day 15 + 7
9. Tumor measurement	CT-scan or MRI in patients with evaluable tumor masses; PET-scan if deemed necessary for proper response assessment	Every 6 -8 weeks
8. Plasma M-component and/or BJ proteinuria	In patients with multiple myeloma	Only on day 1, 22, then every 3 weeks.

Days 1, 8, 15 and 22 of the first 21 days (first cycle), then every 3 weeks

9. Bone marrow biopsy	If deemed necessary for the assessment of disease response	Only at day 43 (if positive at baseline), then at the investigator's discretion
10. Bone imaging in MM patients	Skeletal X-ray / MRI	Every 6 months in case of response
10. Other Investigations	As clinically or biologically indicated.	-

*Additional collection of TEAEs during telephone calls by study nurses at days 4-5 and 11-12. Recording of TEAEs by the investigator will be performed using patient's interrogatory during study visits and consultation of study nurse notes reporting telephone calls between the visits.

** Additional in case of any NCI-CTCAE grade 4, or fever/infection, or bleeding, as clinically indicated but at least twice weekly until recovery of NCI-CTC grade ≤ 1 .

*** Additional in case of NCI-CTC grade ≥ 3 as clinically indicated but at least twice a week until recovery of NCI-CTC grade ≤ 1 . All patients with specific liver test abnormalities (see Section 5.2.4) should be monitored weekly until all abnormalities return to normal or to the baseline state. For patients with isolated total bilirubin increases $\geq 2 x$ ULN or 2 x baseline (if elevated at baseline), except if associated with direct bilirubin \leq ULN, monitoring should be every 2 weeks until bilirubin returns to normal or to the baseline state. DILI may develop or progress even after the causative drug has been stopped.

[§]*Day 8 bone marrow aspiration for patients with AL: 2 tubes of 3mL to be kept for cellular PK/PD.*

PARAMETERS	INVESTIGATIONS	TIMING
1. Clinical Examination	Weight, vital signs, ECOG PS, clinical tumor measurement, and physical examination. Concurrent illness; concomitant medications,	35 + 5 days from last study treatment administration
2. Cardiac function	ECG Echocardiography (LVEF measurement)	35 + 5 days from last study treatment administration
3. Adverse Events	Adverse events occurring on study must be followed up until resolution to NCI-CTC grade ≤ 1 or sequella Serious adverse events have to be declared up to 30 days after last OTX015/MK-8628 intake regardless of relationship with study drugs and beyond if drug related.	35 + 5 days from last study treatment administration
4. Hematology	CBC with platelets counts, WBC differential, hemoglobin and INR.	35 + 5 days from last study treatment administration
5. Biochemistry	LDL, HDL, β2-microglobulin (for patients with myeloma), AP, LDH, CPK, CRP, ASAT, ALAT, total bilirubin, serum creatinine, ionogram (sodium, potassium, chloride, HCO3-), calcium, phosphorus, magnesium, total protein, albumin, glucose.	35 + 5 days from last study treatment administration
6. Urinalysis	Dipsticks for albumin, blood and glucose	35 + 5 days from last study treatment administration
6. Tumor assessment	CT-scan or MRI (baseline) if evaluable tumor massesBone marrow biopsy if necessary for tumor assessment	35 + 5 days from last study treatment administration
7. Plasma M- component and/or BJ proteinuria	In patients with multiple myeloma	35 + 5 days from last study treatment administration

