Complete blood cell counts (CBC): platelets, WBC and differential and hemoglobin, INR, will be performed within 7 days prior to the first study drug administration, then at day 1, then weekly during the first 3 weeks and then every 3 weeks thereafter. In case of grade >2 hematologic toxicity CBC will be performed twice a week until recovery to grade ≤ 2 . In case of neutropenia/thrombocytopenia grade 4, CBC will be performed at least every other day until recovery to grade ≤ 3 . In addition, in case of thrombocytopenia grade 4 lasting ≥ 3 days, a bone marrow aspiration is to be performed. In case of fever $\geq 38^{\circ}$ C, infection, purpura or bleeding, additional CBC should be done as clinically indicated.

• Biochemistry:

LDL, HDL, β 2-microglobulin (only for patients with myeloma),Serum creatinine, glucose, ionogram (sodium, potassium, chloride, HCO₃. (bicarbonate)), calcium, phosphorus, magnesium, total protein, albumin, AP, ASAT, ALAT, total bilirubin, LDH, CPK and CRP will be performed within 7 days prior to the first OTX015/MK-8628 intake, then at day 1, then weekly during the first 3 weeks, and then every 3 weeks thereafter.

In addition, apolipoprotein A-1 (Apo A1) will be assessed within 7 days prior to first OTX015/MK-8628 intake and at day 22 only

• Urinalysis:

Dipsticks for protein, glucose and blood at day 1, 2, 8, 15, 22, then every 3 weeks

Efficacy parameters

- Tumor response will be evaluated using standard criteria for lymphoma, acute leukemia and multiple myeloma.
- Any clue of anti-tumor activity will be quantified and recorded, even though it does not meet criteria for response
- Overall survival (OS)

Statistical considerations:

This is an exploratory Phase I study aimed to assess the pharmacological effects of OTX015/MK-8628 in humans with hematological malignancies. The small subject sample size by cohort does not allow for statistical hypotheses. The decisions will be taken by a board of experts (SMC) and the recommended dose will be validated in further studies.

Study duration and dates	Enrolment: 24-26 months according to the number of DLs explored.
	First-patient in: January 2013
	Last patient in: December 2014- January 2016 End of study follow-up: January – May 2016

ONCOETHIX Clinical Study Protocol OTX015_104 CONFIDENTIAL Date: 18 December 2015

Document Status: Version J

STUDY SCHEDULE

Overall Study Flow Chart

PARAMETERS	BASELINE		DURING STUDY TREATMENT				END OF STUDY TREATMENT

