5.2.4.2 Dose adaptation

Study product dosing (OTX015/MK-8628) will be interrupted in the event of AEs corresponding to the definition of a DLT (see section 3.2), but regardless of the cycle in which they occur:

Non hematological toxicity

- Any grade 3 or 4 non-hematological event (regardless of duration), unless it was not optimally treated with supportive care (e.g. grade 3 vomiting not adequately treated according to antiemetic standard of care).
- Grade 3-4 asymptomatic laboratory abnormal values lasting > 7 days. This definition applies for patients with lab values grade ≤ 1 at baseline. For patients with grade 2 values at baseline, only grade 4 lasting > 7 days will be considered DLT, unless the SMC considers the event clinically significant. See below for liver function tests*.

- Any prolonged grade 2 toxicity (lasting more than 2 weeks) leading to treatment interruption and/or dose reduction.
- * Any of the following liver test abnormalities** (see Appendix 16.12)
 - ALT or $AST > 8 \times ULN$
 - ALT or AST $> 5 \times ULN$ for > 2 weeks
 - ALT or AST > 3 x ULN AND (total bilirubin > 2 x ULN OR INR > 1.5)
 - ALT or AST > 3 x ULN with the appearance of fatigue, nausea, vomiting, right upper quadrant pain or tenderness, fever, rash and/or eosinophilia (> 5%), unless the investigator assesses the rash or fatigue to be related to OTX015 and not related to liver impairment with sponsor's agreement.

**Note: All patients with these liver test abnormalities should be monitored weekly until all abnormalities return to normal or to the baseline state. For patients with isolated total bilirubin increases >2 x ULN or 2 x baseline (if elevated at baseline), except if associated with direct bilirubin \leq ULN, monitoring should be every 2 weeks until bilirubin returns to normal or to the baseline state. Drug induced liver injury (DILI) may develop or progress even after the causative drug has been stopped. Results should be recorded on the CRF and in the database. See guidelines on the handling of these events (potential Hy's law cases).

Hematological toxicity

Patients with AL

• Pancytopenia with a hypocellular bone marrow and no marrow blasts lasting for ≥ 6 weeks after the start of a cycle.

Patients with other hematological malignancies

- Any grade 3 neutropenia, with fever or infection
- Any grade 3 thrombocytopenia with bleeding,
- Any grade 4 neutropenia or thrombocytopenia, regardless of symptoms and lasting \geq 3 days.

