11.5 SAMPLE SIZE JUSTIFICATION

There is no justification of the sample size.

Approximately 50 to 75 evaluable patients, depending on the number of DL in the dose escalation part and number of patients at each DL, are planned.

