# **12.6.2** Individual patient changes

A listing of patients with worsening hematology or biochemistry parameters on study will be provided (baseline grade, worst grade, % decrease).

For thrombocytopenia, description of nadir (duration) and recovery (time to recovery) will be provided. A listing of patients experiencing thrombocytopenia during the study will be provided.

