# 12.6.3 Individual clinically significant abnormalities

For each hematology and chemistry parameter, number and percentage of patients with at least one clinically significant value (according to the investigator) during the study as well as number and percentage of patients with at least one NCI-CTCAE worst grade of 3 to 5 during the study will be presented by DL.

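### From cycle 2, routine blood counts and chemistry under 14/21 follow 7 drug-free days while those under 21/21 are on drug, so whole-study worst-grade laboratory tables may understate 14/21 toxicity relative to 21/21

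*Protocol*

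**What the plan says.** Timing. The on-treatment visit table in Protocol 7.2.2 applies to "Days 1, 8, 15 and 22 of the first 21 days (first cycle), then every 3 weeks", and it times counts and chemistry "Before study treatment administration". The synopsis (Laboratory tests) agrees: counts are taken "then at day 1, then weekly during the first 3 weeks and then every 3 weeks thereafter", and chemistry likewise. Protocol 5.2.3 fixes the cycle at 21 days and equates day 22 with day 1 of the next cycle.

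Schedules. The headers in SAP 6.1 show 14-21 and 21-21 cohorts in both subsets (acute leukemia, AL, and other hematologic malignancies, OHM). OHM also has 5-7 and 7-21 cohorts. All expansion patients are on 14-21.

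Use of the values. Protocol 5.2.4.2 applies the toxicity criteria for interruption to events that meet the DLT definition, "but regardless of the cycle in which they occur". SAP 12.6.3 says that the "number and percentage of patients with at least one NCI-CTCAE worst grade of 3 to 5 during the study will be presented by DL". SAP 12.6.2 adds: "For thrombocytopenia, description of nadir (duration) and recovery (time to recovery) will be provided"; the matching Table vi-3 in SAP 16.1 part B is for OHM only. SAP 12.4 gives the adverse event tables for all cycles and for cycle 1. No such split is planned for the laboratory tables.

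**The concern.** One calendar serves regimens with different dosing patterns. In cycle 1, days 8 and 15 fall on drug, or on the day after the last dose, under both 14/21 and 21/21. After that, the only routine visits come at the end of each 21-day cycle. Under 14/21 that is the end of the rest week, when counts and chemistry have had most time to recover. Under 21/21 it is one more on-drug value.

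The SAP then places worst grades from these two kinds of sample in adjacent columns. At 120 mg QD in OHM, the columns differ only in schedule. No test is planned, but side-by-side description is how readers will judge whether an intermittent schedule is better tolerated. Part of any apparent advantage could come from when the samples were taken.

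The adverse event tables only partly compensate. Protocol 7.3.2.2 keeps grade 3-4 laboratory changes without clinical consequences out of the adverse event pages, so for asymptomatic cytopenia the laboratory tables are the main record.

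**Working it through.** **1. Drug-free days before each scheduled pre-dose sample** (Protocol 5.2.3 and 7.2.2).

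| Schedule | Day 8 | Day 15 | Day 22 | Day 43 | Day 64 |
|---|---|---|---|---|---|
| 14/21 | 0 | 0 | 7 | 7 | 7 |
| 21/21 | 0 | 0 | 0 | 0 | 0 |
| 7-21, if 7 on, 14 off | 0 | 7 | 14 | 14 | 14 |
| 5-7, if 5 on, 2 off | 2 | 2 | 2 | 2 | 2 |

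The 14/21 row reproduces the protocol's own 7-day rest period. The last two rows are readings of the labels, which the documents do not define. Under 14/21 the day 22 sample comes 8 days (192 h) after the last dose. At the longest mean plasma half-life in Protocol 1.1.3 (16.3 h, healthy volunteers, another formulation), 2^(-192/16.3) is under 0.03% of the drug, so this is an off-drug value.

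**2. Patients by initial schedule** (column Ns in SAP 6.1).

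- AL 14/21: 3+3+4+4+8+7+7+19+16 = 71. AL 21/21: 3+6 = 9. Sum 80.
- OHM 21/21: 5+3+4+7+6+7 = 32. OHM 14/21: 3+16 = 19. 5-7: 5. 7-21: 5. Sum 61.
- Total 80+61 = 141, as in SAP 7. On 14/21: 71+19 = 90. On 21/21: 9+32 = 41.

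**3. How much a whole-study worst value could lose.** The documents give no nadir or recovery time, so both models below are assumptions that show a range.

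*Model A: the same toxicity repeats each cycle.* The depression builds up on drug and decays off drug with half-time h days; 1 is the plateau under continuous dosing.

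- Cycle 1 day 15 value: 1 - 2^(-14/h).
- Later-cycle peak at steady state: (1 - 2^(-14/h)) / (1 - 2^(-21/h)).
- Share of a later peak still visible after 7 days off: 2^(-7/h).
- Recorded worst over the study as a share of the true worst: cycle 1 day 15 divided by the later peak, which is 1 - 2^(-21/h).

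| h (days) | Later peak visible after rest | Recorded worst / true worst, 14/21 |
|---|---|---|
| 2 | 9% | 100% |
| 3 | 20% | 99% |
| 5 | 38% | 95% |
| 7 | 50% | 88% |
| 10 | 62% | 77% |

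Under 21/21 the recorded worst is 100% throughout. The first column describes single later-cycle visits. The second describes the worst-grade tables, and it is much milder because cycle 1 day 15 is sampled.

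*Model B: grade 3-4 arises independently in each cycle.* Assume 20% per cycle over 4 cycles, with cycle 1 always seen and later events seen with probability v.

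- v = 1: 1 - 0.8^4 = 59% of patients.
- v = 0.5: 1 - 0.8 × 0.9^3 = 42%.
- v = 0: 20%.

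The understatement thus runs from nil (A, fast recovery) to about two thirds of affected patients (B, no later event seen: 20% recorded against 59%).

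**4. Routes by which later-cycle values on drug, or extra values, still arise.**

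- Protocol 6.3.2: at least weekly counts for patients on anticoagulant or antiaggregant therapy.
- Flow chart footnote (text broken in extraction): chemistry repeated weekly after grade ≥2 toxicity in the first cycle.
- Protocol 5.2.4.1: AL patients could be offered continuous dosing after an intermittent cycle without DLT.
- Event-triggered tests, which start only once an abnormality or symptom has been noticed.

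The trigger rules differ. The synopsis starts twice-weekly counts above grade 2 and continues them to grade ≤2, with at least every-other-day counts for grade 4 neutropenia or thrombocytopenia until grade ≤3. The 7.2.2 footnote starts at grade 4, fever/infection or bleeding, and continues at least twice weekly to grade ≤1.

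**The case against.** The strongest reply is that little rests on these tables. DLT is a cycle 1 endpoint, the recommended dose is already set, and SAP 6.1 plans no tests. SAP 12.6.1 describes every parameter by visit, so days 8, 15 and 22 can be read by schedule, and 12.6 lists all values. Clinically significant laboratory abnormalities also reach the adverse event tables, which have a cycle 1 version; Protocol 8.2 defines that class more widely than 7.3.2.2. This limits the point to reporting. It does not remove it: by-visit summaries do not give a worst grade per patient over a common window.

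The second reply concerns AL. Protocol 1.2.5 says that counts are usually extremely low at entry and cannot be used to judge marrow toxicity. The AL haematological criterion rests on marrow findings at days 22 and 43 (3.2.2.1). This stands: the haematology point is essentially an OHM point, although chemistry applies to both subsets. The OHM comparison at one dose is also small, 3 patients on 14/21 against 7 on 21/21 at 120 mg.

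A reader might infer that every later-cycle sample is off drug, that nadirs are missed, and that the tables favour intermittent dosing in general. The documents do not support that. The exceptions above contradict 'every', no nadir timing is given, and 5-7 may leave only 2 drug-free days. Nor can the share of a deficit visible after the rest week be read as the bias in the worst-grade tables, since the cycle 1 end-of-dosing value already enters them.

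**Conclusion.** The mismatch in sampling time is a fact of the calendar. The resulting bias is a possibility of known direction and unknown size. From cycle 2, routine samples under 14/21 follow 7 drug-free days and those under 21/21 do not, apart from the stated exceptions. The whole-study worst-grade tables and the OHM thrombocytopenia nadir and duration table may therefore understate 14/21 toxicity relative to 21/21. This bears on 19 OHM patients against 32 for haematology, and on 90 against 41 across both subsets for chemistry, counted by initial schedule.

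The size depends on recovery speed and on whether severe values recur by chance in later cycles; neither is in the documents. A reader might also infer that the recommended dose is undermined. It is not: cycle 1, DLT and the DLT-based rule are essentially unaffected. The point is a worthwhile and cheap improvement to the reporting.

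**What to change.** In SAP 12.6 and Tables vi-1 to vi-6 of 16.1 part B:

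- Add a cycle 1-only version (values to day 22) of the worst-grade and thrombocytopenia outputs, as is already done for adverse events.
- Name that version as the one for any comparison between schedules. Its day 8, 15 and 22 calendar is common to all of them.
- Footnote the all-cycle tables to say that routine values from cycle 2 on 14/21 are taken after the rest week, with the exceptions listed above.

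The synopsis and the 7.2.2 footnote must also be reconciled on when extra counts start and stop, so that the report can state which rule governed the unscheduled values.

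The cost is SAP wording and a repeat of existing programs on collected data; SAP 16.1 allows changes to the data presented during programming. The downside is more output pages and fewer values per patient in the comparison tables. Changing visit timing in the protocol would not help, because SAP 5 states that the study is complete and missing later-cycle values cannot be recovered.

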3.2.2.2 In patients with other hematological malignancies

- Any grade 3 neutropenia, with fever or infection; any grade 3 thrombocytopenia with bleeding,
- Any grade 4 neutropenia or thrombocytopenia, regardless of symptoms and lasting \geq 3 days.

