#### Laboratory tests

• *Hematology*:

Complete blood cell counts (CBC): platelets, WBC and differential and hemoglobin, INR, will be performed within 7 days prior to the first study drug administration, then at day 1, then weekly during the first 3 weeks and then every 3 weeks thereafter. In cases of grade >2 hematologic toxicity CBC will be performed twice a week until recovery to grade  $\leq 2$ . In case of neutropenia/thrombocytopenia grade 4, CBC will be performed at least every other day until recovery to grade  $\leq 3$ . In addition, in cases of thrombocytopenia grade 4 lasting > 3 days, a bone marrow aspiration is to be performed. In cases of fever  $\geq 38^{\circ}$ C, infection, purpura or bleeding, additional CBC should be done as clinically indicated.

• Biochemistry:

LDL, HDL,  $\beta$ 2-microglobulin (only for patients with myeloma), serum creatinine, glucose, ionogram (sodium, potassium, chloride, HCO3. (bicarbonate)), calcium, phosphorus, magnesium, total protein, albumin, AP, ASAT, ALAT, total bilirubin, LDH, CPK and CRP will be performed within 7 days prior to the first OTX015/MK-8628 intake, then at day 1, then weekly during the first 3 weeks, and then every 3 weeks thereafter. In addition, apolipoprotein A-1 (Apo A1) will be assessed within 7 days prior to first OTX015/MK-8628 intake and at day 22 only.

• Urinalysis:

Dipsticks for protein, glucose and blood at day 1, 2, 8, 15, 22, then every 3 weeks.

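### Protocol 7.2.2 sets lower blood-count minimums in severe cytopenia than the protocol synopsis, and none beyond routine visits for uncomplicated grade 3

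*Protocol*

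**What the plan says.** **Protocol 7.2.2, footnote to the Hematology row.** "Additional in case of any NCI-CTCAE grade 4, or fever/infection, or bleeding, as clinically indicated but at least twice weekly until recovery" to grade 1 or lower. Nothing is added for grade 3 without fever, infection or bleeding. Routine visits are on "Days 1, 8, 15 and 22 of the first 21 days (first cycle), then every 3 weeks".

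**Protocol synopsis, Laboratory tests.** There are two tiers. "In case of grade >2 hematologic toxicity CBC will be performed twice a week until recovery to grade" 2 or lower. For grade 4 neutropenia or thrombocytopenia, "CBC will be performed at least every other day until recovery to grade" 3 or lower. For fever, infection, purpura or bleeding it leaves extra counts to clinical judgment, with no number.

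**SAP synopsis, Laboratory tests.** It repeats the protocol synopsis: "In case of neutropenia/thrombocytopenia grade 4, CBC will be performed at least every other day until recovery to grade" 3 or lower.

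**Rules that depend on these counts.** In patients with other hematological malignancies (OHM), Protocol 3.2.2.2 counts as a DLT "Any grade 4 neutropenia or thrombocytopenia, regardless of symptoms and lasting" at least 3 days. Under Protocol 5.2.4.2, dosing "will be interrupted in the event of AEs corresponding to the definition of a DLT (see section 3.2), but regardless of the cycle" in which the event occurs.

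**Exception.** Protocol 6.3.2 asks for counts in patients on anticoagulants or antiaggregants "at least weekly during the whole study, and more in case of grade 2 to 3 thrombocytopenia".

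**The concern.** Sites are likely to schedule tests from the visit table. A site working from 7.2.2 alone would meet that table and still breach the synopsis, in two places.

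At grade 4, counts could be 3 or 4 days apart where the synopsis allows at most 2.

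At uncomplicated grade 3, no further count is required until the next routine visit. This matters more, because grade 3 is where closer counting would catch a fall to grade 4. In OHM patients, grade 4 lasting at least 3 days requires dose interruption in any cycle. From day 22 such an episode could begin and end between required counts while dosing continues.

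The grade 3 omission looks unintended, though this is inference. The biochemistry footnote in the same table starts extra testing at grade 3, while the hematology footnote starts at grade 4. Low platelets were also foreseeable, since Protocol 1.1.2.5 reports falls in both rats and dogs.

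At stake are the safety monitoring of severe cytopenia, one rule across sites and, to a limited extent, the dating of thrombocytopenia in SAP 12.6.2 and Table vi-3.

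**Working it through.** The plan gives no figure to reproduce. The check sets the rules side by side and then does arithmetic on the gaps.

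**1. The rules compared**

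| Situation | Protocol synopsis | Protocol 7.2.2 |
|---|---|---|
| Grade 4 neutropenia or thrombocytopenia | every other day to grade ≤3, then twice a week to ≤2 | twice weekly to ≤1 |
| Grade 3, uncomplicated | twice a week to ≤2 | routine visits only |
| Other hematological grade 4 | twice a week to ≤2 | twice weekly to ≤1 |
| Fever, infection, bleeding | clinical judgment, no number | twice weekly to ≤1 |

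The footnote is lower in the first two rows on frequency. It is stricter in how long monitoring lasts, in putting every grade 4 under a rule that runs to grade ≤1, and in giving complications a fixed floor.

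**2. Delay to the next count**

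Assumptions: twice weekly means alternating gaps of 3 and 4 days; the change of grade is equally likely at any time; the site does only the minimum. Then mean delay = Σ(gap²) / (2 × Σ gap), and maximum delay = longest gap.

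| Schedule | Mean delay (days) | Maximum (days) |
|---|---|---|
| Every other day | 4/4 = 1.0 | 2 |
| Twice weekly | (9 + 16)/14 = 1.8 | 4 |
| Weekly (cycle 1 visits) | 49/14 = 3.5 | 7 |
| Every 3 weeks (from day 22) | 441/42 = 10.5 | 21 |

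- *Grade 4, recovery to grade ≤3:* mean 1.0 day (synopsis) v 1.8 days (7.2.2); maximum 2 v 4.
- *Uncomplicated grade 3, fall to grade 4:* mean 1.8 days (synopsis) v 3.5 days in cycle 1 and 10.5 days from day 22 (7.2.2); maximum 4 v 7 and 21.

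**3. Does the synopsis rule confirm a 3-day episode sooner?**

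Take the first grade 4 count as day 0. Every other day gives counts on days 2 and 4, so the first pair at least 3 days apart is complete on day 4. Twice weekly completes it on day 3 or day 4, depending on the first gap. The synopsis rule is no faster.

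**4. Effect on the thrombocytopenia outputs**

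Table vi-3 lists the duration of grade 3 or 4. If that is one combined duration, it ends at grade ≤2. A patient coming down from grade 4 through grade 3 is counted twice weekly on that last step under both rules, so the end date gains little. The gain is in time spent at grade 4 and in episodes that peak at grade 3, where 7.2.2 leaves only routine visits.

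**5. Counts needed after the first grade 4 count**

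Within 7, 14 and 21 days: every other day 3, 7 and 10; twice weekly 2, 4 and 6.

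**The case against.** Both texts are minimums, and the footnote invites more counts where clinically indicated. A site can meet both, and the synopsis is part of the same protocol. Section 7.2.2 itself asks for marrow aspiration when grade 4 thrombocytopenia lasts more than 3 days, so sites must follow duration anyway. The SAP synopsis only restates the protocol and does not govern site conduct, so it is not independent evidence. The flow-chart footnote on blood counts is cut off in the available text; if it repeats the synopsis tiers, sites had a second reminder. The 3.5- and 10.5-day figures describe a site that orders nothing beyond the table. All of this stands. It limits the consequence but does not make the texts agree.

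Three stronger readings are tempting and not supported.

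- *The footnote is simply the weaker rule.* It is stricter in the three respects listed in the working. Continuing to grade ≤1 also suits Protocol 5.2.4.2, where dosing resumes below grade 2 or at baseline.
- *Gaps of 3-4 days, as long as the 3-day DLT criterion, mean that DLTs were misclassified.* Confirmation is no faster under the synopsis, the documents state no convention for dating the start and end of an episode, and they do not say how often such episodes occurred. The criterion applies only to OHM patients, 61 of the 141 enrolled (SAP 6.1 and 7); the hematological DLT in acute leukemia rests on marrow findings at days 22 and 43.
- *All thrombocytopenia durations would be dated better.* The end of a combined grade 3-4 episode would hardly change.

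**Conclusion.** The inconsistency is real and should be corrected as a safety-monitoring point. For grade 4 neutropenia or thrombocytopenia, 7.2.2 allows a longest gap of 4 days against 2, and a mean delay of 1.8 days against 1.0 in seeing recovery to grade ≤3. For uncomplicated grade 3 it allows 7 days in cycle 1 and 21 days from day 22, against 3-4 days. The grade 3 omission is the more important, because a fall to grade 4 requiring dose interruption in OHM patients could be missed. Patients on anticoagulants or antiaggregants are excepted by 6.3.2.

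The sizes rest on evenly spread twice-weekly counts, uniform timing of the change of grade, and a site working to the 7.2.2 minimum. The number of patients affected cannot be derived from the documents. No stated figure or decision rule changes, and no reduction in DLT misclassification is shown. SAP section 5 says the study is complete, so a correction helps only patients still on treatment under this version, or a later protocol that reuses the table.

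**What to change.** Reword the hematology footnote in Protocol 7.2.2 as three tiers:

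- Grade 4 neutropenia or thrombocytopenia: a count at least every other day until grade ≤3, then at least twice weekly until grade ≤1.
- Any other grade 4, fever/infection or bleeding: according to clinical need, and never less than twice weekly, until grade ≤1.
- Grade 3: at least twice weekly until grade ≤2.

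This carries over the synopsis frequencies and keeps what is stricter in the footnote.

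Decide also whether the every-other-day tier is meant for acute leukemia patients who enter with disease-related grade 4 counts; Protocol 1.2.5 says their counts are usually extremely low at entry. If it is not, say so in both the synopsis and 7.2.2.

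The cost is one footnote and, against the 7.2.2 minimum at grade 4, 3 v 2 counts in the first 7 days, or 10 v 6 if grade 4 persists for 21 days. The longer case would arise mainly in acute leukemia. In the other malignancies it is a few counts per episode. The synopsis already requires all of these counts.
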